8.4.2 Risk Assessment

All treatment and assessment activities in the proposed research present no more than minimal risk to study participants. Children will have one-on-one supervision at all times during the assessment and treatment procedures by a licensed pediatric physical therapist. Risks include those involved with any pediatric physical therapy session or toddler play session, including bumps and bruises from falling or crashing into toys, and the unlikely possibility of muscle strain or soreness from overuse. The environment will be prepared such that only items safe for toddlers and young children will be in the treatment and assessment areas.

DSM treatment, which encourages falling, will occur over a floor of thin rubber mats to minimize the impact of falls. The weight support harness for DSM therapy is custom-made for the target age range, includes special provisions for small bodies and sensitive skin, such as narrow straps and use of neoprene, and will also prevent the impact of falls. The harness may prevent or reduce the impact of falling. Parents will be advised to dress the children in slim-fitting garments that have sleeves and their axilla areas will be checked periodically to assure that there is no skin redness from the harness. If children experience any discomfort with the harness, it will be repositioned until it is comfortable.

Additionally, protected health information will be collected as part of study records, and breaches of this information outside of the study team resulting in loss of confidentiality is an unlikely but potential risk. We will follow CHOP policies to ensure compliance with HIPAA and IRB regulations for safeguarding participant information to protect against loss of confidentiality. Electronic data will be stored in secure, HIPAA-compliant, password-protected systems. Hard copies of data collection instruments and training logs will be stored in a locked cabinet in the PI's locked office. Participants will be assigned a unique identifier that contains no protected health information. Access to the identifiers of the coded data will be controlled by the PI and only study team members will have access to the electronic and paper data. All members of the study team will undergo Human Subjects Research training.

All adverse events will be reported in accordance with IRB and NIH requirements. All risks and alternative treatment options will be explicitly stated in consent documents.

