CONV treatment. The conventional treatment group will receive traditional, therapist-directed pediatric physical therapy. Therapy will focus on early gait training strategies and encouragement of "normal" movement patterns for walking and other age-appropriate movements, with manual guidance or correction of atypical movements from the therapist. This group may use assistive devices, orthoses, and may receive static body weight support for gait training. Therapy activities will be performed in blocks of practice, with the specific activities and level of therapist assistance tailored to each child. Examples include: using a posterior rolling walker with ankle foot orthoses (braces), physically guided practice of standing from the floor through half kneeling, manual correction of side steps while cruising at a bench, and repeated sit to stand practice from a small chair. The distinguishing characteristics of each treatment are listed in Table 4.

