5.2.6 Possible video or photograph

One treatment session will be videotaped each week to quantify participant error experience (number of falls), motor variability (time spent in one motor activity before moving to the next), and salience or motor engagement (time engaged in a dynamic motor activity) during DSM treatment, allowing evaluation of the relationship of these factors to treatment response. The videotaped sessions will also be coded for the amount of time participants spend doing activities in each of the GMFM subscales, to allow evaluation of the relationship between time spent in each activity category and outcome in each subscale. Randomly selected videos will also be used for quality checks to ensure that the two treatments remain different and consistent with the distinguishing characteristics of each group.

Occasional photographs may be taken, if separate consent is provided, for educational or scientific purposes, or as souvenirs for the children.

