5.3 Safety Evaluation

Subject safety will be monitored by adverse events. Anticipated and unanticipated adverse events will be recorded to confirm that DSM treatment does not pose greater risks than current interventions.

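### The only written skin check covers the DSM harness, so the Hypothesis 2.1 adverse-event comparison is open to unequal detection if skin redness is recorded as an event

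*Combined protocol and SAP*

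**What the plan says.** **Skin check.** Section 8.4.2 introduces the device with "The weight support harness for DSM therapy is custom-made for the target age range". It then gives clothing advice, the check ("their axilla areas will be checked periodically to assure that there is no skin redness from the harness") and repositioning if the child is uncomfortable. No other harness is mentioned there, and no other skin check appears in the protocol.

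**CONV exposure.** Section 3.1.2 on CONV treatment: "This group may use assistive devices, orthoses, and may receive static body weight support for gait training". How many children will use such support is not stated.

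**Capture of adverse events.** Section 5.3: "Anticipated and unanticipated adverse events will be recorded to confirm that DSM treatment does not pose greater risks than current interventions". Section 7.1 adds only that events are monitored throughout. Neither section defines an adverse event, says whether redness is one, or describes how events are elicited.

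**Judgement.** Section 6.2.3 presents types and frequencies descriptively by treatment and treats a difference below 10% as similar. Hypothesis 2.1 belongs to Aim 2, one of the two primary aims in section 2.1.

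**Common to both arms.** Supervision is one-to-one by a licensed therapist (8.4.2). A training log is kept for every session, and one session a week is filmed with consent (3.1.2). The study team meets every two weeks on safety and progress (8.4.1).

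**The concern.** Redness under clothing and straps is usually found by looking. The protocol writes down an instruction to look in one arm only, while the other arm may also be in weight support. A comparison of recorded events can then differ because of how they were sought, not because risk differs.

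The rule in section 6.2.3 has no confidence interval, so a few recorded cases can decide it. Masking does not protect the comparison during treatment: the same therapists deliver both interventions, and the blinded assessor in section 3.2 collects the outcome measures. The trigger in section 8.4.1 for appointing a Study Monitoring Committee (events in more than 15% of all participants) also depends on what is detected. Unequal ascertainment cannot be repaired once the data are collected.

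**Working it through.** **The plan's own figure.** Section 6.3 gives no event rate, power or precision for Hypothesis 2.1. Its one precision figure concerns GMFM-66: 1.96 × 9 × √(2/17) = 6.05, which reproduces the stated ±6 but says nothing about adverse events.

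**Step 1: how many children decide the verdict.** I take frequency to mean the proportion of children with at least one event (an assumption; section 6.2.3 does not say). Section 6.3 gives 21 per arm and 17 after attrition. The 60 enrolled in section 3.3.2 would give 30 per arm if split equally (also an assumption).

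- 17 per arm: 1/17 = 5.9%, 2/17 = 11.8%. Two extra children cross the limit.
- 21 per arm: 2/21 = 9.5%, 3/21 = 14.3%. Three cross it.
- 30 per arm: 2/30 = 6.7%, 3/30 = 10.0%. Three reach it, and 10.0% is not below 10%.

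**Step 2: expected spurious gap.** Let p be the true proportion of children with a recordable event, equal in both arms. Let detection be complete in DSM and a fraction s in CONV. The expected gap is p − ps = p(1 − s). It reaches 10 points when p = 0.10/(1 − s): 14.3% for s = 0.3, 20% for s = 0.5 and 33.3% for s = 0.7. The documents give neither p nor s.

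**Step 3: chance of a false DSM excess.** With 21 per arm, take X ~ Bin(21, p) for DSM and Y ~ Bin(21, ps) for CONV. The table gives the exact P(X − Y ≥ 3).

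| p | expected gap, s = 0.5 | s = 1 | s = 0.5 |
|---|---|---|---|
| 5% | 2.5 points | 0.04 | 0.06 |
| 10% | 5 points | 0.10 | 0.19 |
| 20% | 10 points | 0.17 | 0.43 |
| 30% | 15 points | 0.20 | 0.60 |

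**Step 4: the rule is noisy even with equal detection.** With s = 1, a gap of 10 points or more in either direction occurs with probability 0.07, 0.19, 0.33 and 0.40 at the same four values of p. Equal ascertainment removes the bias, not this noise.

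**Step 5: masking a CONV excess.** Suppose true proportions of 10% in DSM and 30% in CONV (assumed). With full detection, P(|X − Y| ≤ 2) = 0.24. With half detection in CONV (15% recorded), it is 0.71. A real CONV excess would then usually be called similar.

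**The case against.** **Falls.** A reader might infer that falls are a second harm sought only in DSM, because weekly video counts them "during DSM treatment, allowing evaluation of the relationship of these factors to treatment response". The documents do not support that. Section 8.4.2 speaks of "DSM treatment, which encourages falling, will occur over a floor of thin rubber mats to minimize the impact of falls". Falling is part of the intervention, and the count measures motor error for Hypothesis 1.2. Nothing sends it to the adverse-event record. The harm that section 8.4.2 names is bumps and bruises, as a risk of any therapy or play session, and no difference between arms in looking for those is shown.

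**CONV children as unobserved.** This too goes beyond the text. Supervision, session logs and adverse-event monitoring apply to both arms, and the same therapists treat both. Only a specific written skin check is missing. These safeguards do not close the gap, because none directs anyone to the skin, and log and video review in section 8.4.1 serves treatment fidelity.

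**Redness may never reach the count.** The check can be read as comfort care for one device, and no passage says that redness is an adverse event or who records events. If it is not recorded, the check adds nothing to Hypothesis 2.1. This stands, which is why the point is conditional. The silence itself needs resolving.

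**Size.** Section 8.4.1 expects few events. The calculation assumes complete detection from a check that is only periodic, and equal true risk although all DSM treatment time is spent in weight support and CONV use is optional. This also stands: the figures are illustrations. Presenting events by type would help a reader to see a skin imbalance, but not to tell whether it came from detection.

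**Unseen material.** The training log form, the study manual and Tables 1 and 4 are not in the text reviewed and might contain a common prompt.

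**Conclusion.** The point holds in a limited form. The written skin check is tied to the DSM harness, CONV children may also be in weight support, and no common method of finding adverse events is stated. If redness is recorded as an adverse event, Hypothesis 2.1 may be biased. It would be too strong to say that it is biased, because the definition of an event, the event rate and the use of support in CONV are all unknown.

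The likely direction is more recorded events in DSM, or a CONV excess that goes unseen. The mechanism works against DSM, so it would not be expected to conceal a DSM harm. Three extra detected cases at 21 per arm settle the verdict. The effect is small at an assumed rate near 5% and substantial at 20% or more with half detection. The change is worth making because it is cheap and must be made before data are collected.

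**What to change.** 1. In sections 5.3 and 6.2.3, define an adverse event and state whether skin redness and fall-related injury count.
2. Add one identical checklist (skin redness, bump or bruise, soreness) to the training log already kept for every session in both arms, and base Hypothesis 2.1 on it.
3. Make the ascertainment and recording of skin findings the same for any child who uses weight support, in either arm. This concerns data collection; what skin care a child needs is for the clinical team.
4. Report device-related skin findings on a separate line and state whether they count towards the 10% rule.
5. Do not count falls themselves as adverse events, because DSM encourages them and counting them would build in an arm difference. Count only resulting injuries.

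The cost is a small form revision and a little time per session, with no new visits or staff. More minor CONV events will be recorded.

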8.4.3 Potential Benefits of Trial Participation

It is unknown whether the functional mobility of the participants will improve as a result of study participation, but evidence suggests that greater physical activity leads to improved motor performance. The results of the pilot study and outcomes of conventional early intervention rehabilitation also suggest that at least modest gains can be expected from participation in either rehabilitation treatment. The knowledge gained will inform early rehabilitation practice for other children with CP and other neurodevelopmental conditions, may lead to the development of other interventions, and the risk to participants is minimal.

8.4.4 Risk-Benefit Assessment

If the study hypotheses are supported, there will be implications for the rehabilitation of individuals with CP and other neurodevelopmental conditions, and the results will likely lead to the development of other interventions, including those that can be conducted in the home and smaller clinical settings. This knowledge is important because CP is the most common cause of physical disability in children, affecting over 10,000 babies each year in the United States, and few interventions exist for meaningful functional improvement. The 15 million individuals who live with CP worldwide experience this physical disability for their entire lifespan. There is no more than minimal risk to study participants, with the potential to learn important information about how to optimize motor development potential in young children with neurological injury. Therefore, the risk to potential benefit ratio for the proposed study is very small, and the potential importance is high.

8.5 Recruitment Strategy

Our goal is to enroll 16 and 20 participants in Years 1 and 2, respectively. The primary avenue for recruitment will be through the Neonatal Follow-up clinic at CHOP, directed by [name]. Eligible patients seen in CHOP's CP clinic and those with CP who are receiving services at the Center for Rehabilitation will also be invited to participate. Potential candidates who are not CHOP patients will be reached through the internet (www.clinicaltrials.gov) and the CHOP Research Institute website (http://www.research.chop.edu/research/clinical_research/) and mailings to local clinicians, including therapists, developmental pediatricians, and pediatric neurologists. All recruitment materials will receive prior ethics approval.

We will also be working with the Recruitment Enhancement Core, including posting messages in the "This Week at CHOP" email to employees. Additionally, we will also work with the National Rehabilitation Information Center (NARIC) to send out notifications regarding our study. For both the "This Week at CHOP" and NARIC postings, we will use the approved blurb below in Section 7.01 (5.0) that is currently used on CHOP's public website.

We will also work with PeRC to distribute mailings to potential participants. PeRC will provide the study team with a list of names and contact information for mailings. Potential participants will be asked to call or email a member of the study team for additional information. Interested participants will be contacted via phone or email for information about the study.

We will also work with Research Communications to create a short video about our study. This video will be distributed to rehabilitation therapists and early intervention agencies at CHOP and in the community outside of CHOP. This video can be shared with colleagues and/or caregivers of potential participants.

8.6 Informed Consent/Accent and HIPAA Authorization

A parent or legal representative of each potential participant will receive a verbal and written explanation of the purposes, procedures and risks of the study. If they are interested, the child will be scheduled for an initial physical therapy examination with the primary

research physical therapist. The therapist will conduct an examination to determine if the child meets the selection criteria. If eligible, the family will have the option to consider participation and later inform the therapist if they choose to participate, or they will be able to sign the informed consent documents at that time. Informed consent will be obtained by the research physical therapist, the trained study coordinator, or an investigator, and will be documented in the electronic database. The family will have the opportunity to ask questions throughout the entire process. The parent or legal representative must provide written informed consent prior to the start of any study activities. Written assents of minors will not be obtained due to the age of the participants.

8.7 Payment to Subjects/Families

8.7.1 Reimbursement for travel, parking and meals

To encourage attendance at scheduled appointments, caregivers of participants will receive \$5 per session to reduce their transportation cost burden (which is \$3 parking for patients and \$2 fuel, or public transportation for the participant and a caregiver at \$3.10 round trip per person within the city). This will be applicable to all visits, including both treatment and assessment sessions. Payment will be made through the ClinCard participant incentive program supported by the Research Institute.

8.7.2 Payments to parent for time and inconvenience (i.e. compensation)

Caregivers of participants will additionally receive \$25 for completion of each of the 8 assessments, including all applicable measures. Payment will be made through the ClinCard participant incentive program supported by the Research Institute.

8.7.3 Payments to subject for time, effort and inconvenience (i.e. compensation)

In accordance with CHOP patient incentive guidelines, no monetary payment will be made to participants as they will be between 1-3 years of age.

8.7.4 Gifts

Participants will receive small tokens of appreciation for participation throughout the study, such as stickers, stuffed animal or other small toys.

9 PUBLICATION

Outcomes will be disseminated to various stakeholders, including pediatric and neurologic clinicians, rehabilitation researchers and parents. Examples of peer-reviewed scientific publications include *Developmental Medicine & Child Neurology*, *Neurorehabilitation and Neural Repair*, *Physical Therapy*, and *Gait & Posture*.

